8.1.3 Electrocardiography (ECG)

A standard 12-lead ECG is expected to have been obtained as part of routine standard of care.

8.1.4 Chest X-ray or lung ultrasound

Evidence of pulmonary congestion on chest X-ray or 2 or more B-lines on lung ultrasound is required for study eligibility.

8.1.5 Worsening heart failure

The physician will evaluate the occurrence of worsening heart failure in the preceding interval (i.e., at Visit 3, the occurrence of WHF between Visit 2 (24 hours post-randomization) and Visit 3 (72 hours post-randomization). The investigator will report all events of worsening signs and/or symptoms of heart failure occurring through day 31 as an adverse event. Worsening heart failure will be evaluated in two ways: (1) for the secondary endpoint, all adverse events of worsening heart failure will be included. (2) for the exploratory endpoints, worsening heart failure that occurs between 24 hours and 7 days after randomization, where both worsening signs and/or symptoms of HF and intensification of therapy for HF including up-titration of intravenous therapy, or mechanical ventilatory, renal, or circulatory support occurred will be included.

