1 PROTOCOL SUMMARY

1.1 SYNOPSIS

- Title:** Effect of Short-Term Prednisone Therapy on C-reactive protein Change in Emergency Department Patients With Acute Heart Failure and Elevated Inflammatory Markers (CORTAHF)
- Study Description:** This is a multicenter, parallel-group, randomized, open-label, controlled trial. Patients with a diagnosis of acute heart failure (AHF) in the emergency department (ED) or after emergency presentation to hospital will be screened and informed of the study. After signed consent, patients will be randomized into the control group (usual AHF treatment) or intervention group (usual AHF treatment + prednisone). Prednisone will be given for 7 days. Patients will be assessed at days 2, 4 or at discharge if earlier, and at day 7 at hospital visit. If the patient has been discharged before day 7, a follow-up visit will be scheduled at day 7 for endpoints assessment followed by a scheduled hospital visit at day 31 and a telephone follow-up at day 91. Study drug will be dispensed for the patient to take home until day 7.
- Objectives:** Primary objective: to assess the effects of prednisone therapy started in the ED/hospital and continued for up to 7 days on the change of CRP level.
- Secondary objectives: to compare the effects of prednisone therapy on the occurrence of death, hospital readmission for HF, or worsening HF (WHF) through day 91; and on change in quality of life (QoL) as measured by the EQ-5D-5L questionnaire at day 7.
- Other objectives include comparisons on the effects on WHF, death or HF readmission through day 31, change in QoL at day 31, symptoms and signs of heart failure at day 7 including weight, and all-cause mortality or hospital readmission for HF through day 91.
- Endpoints:** Primary endpoint: change of CRP level, defined by CRP level at day 7 minus CRP level at inclusion
- Secondary Endpoints:
1. Time to first event of WHF adverse event, death, or hospital readmission for decompensated HF to day 91.
 2. Changes in quality of life measured by the EQ-5D-5L from randomization to day 7.
- Study Population:** 120 adult patients visiting the ED or presenting emergently to the hospital with a diagnosis of AHF and elevated markers of congestion and inflammation.
- Inclusion criteria:
1. Age 18 to 85 years of age
 2. Unplanned ED visit or hospital presentation within the 12 hours prior to Screening with acute or worsening dyspnea and/or orthopnea, and pulmonary congestion on chest X-ray or lung ultrasound.

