11. Renal disease or eGFR < 30 or > 80 mL/min/1.73m² (as estimated by the simplified MDRD formula) at inclusion or history of dialysis.
12. Systemic steroid therapy, within 30 days from inclusion.
13. Inability to consent, or patient under guardianship measure
14. Participation in another intervention trial in the past 30 days
15. Anticipated non-adherence to study protocol or follow-up.
16. Pregnant or nursing (lactating) women.
17. Known hypersensitivity to steroids or constituents of prednisone tablets (excipients)

18. Psychotic states not yet controlled by treatment
19. Concomitant administration of live vaccines and up to 3 months after end of corticotherapy administration.
20. Patient under legal protection measure (tutorship or curatorship) and patient deprived of freedom
21. Persons subject to psychiatric care without their consent

Phase:

N/A

Description of Sites/Facilities

5 hospitals in Armenia

Enrolling Participants:

Description of Study

Investigational product: Prednisone 40 mg once a day, for up to 7 days added to usual care medications.

Intervention:

Comparator: Usual care alone.

[figure not shown]
Study Duration:

13 months (including recruitment (12 months), Follow up (1 month for the last patient enrolled)

Participant Duration:

91 days

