3 OBJECTIVES AND ENDPOINTS

OBJECTIVES	ENDPOINTS	JUSTIFICATION FOR ENDPOINTS
Primary		
To assess the effects of prednisone therapy started in the ED and continued for up to 7 days on the change of CRP level	Change in CRP level at 7 days	CRP levels increase rapidly in response to trauma, inflammation and infection and decrease rapidly with resolution of these conditions (Du Clos 2000). Thus, CRP measurement is widely used to monitor inflammatory states.
Secondary		
To compare the effects on the occurrence of death, hospital readmission for HF or worsening HF (WHF) through day 91	The composite of first event of a WHF adverse event, hospital readmission for HF, or death through day 91	WHF has been shown to be associated with longer hospital stay and increased risk of HF readmission and death, and HF readmission and death are outcomes representing disease progression. The composite is a generally accepted endpoint in AHF trials. For this pilot study, the definition of WHF has been expanded to include all reported adverse events of WHF (not only those requiring intensification of IV therapy or mechanical support) over a broader timeframe (longer than 7 days).
To compare the effects on change in quality of life (QoL) as measured by the EQ-5D-5L questionnaire at day 7	Changes in quality of life measured by the EQ-5D-5L from randomization to day 7	Quality of life, encompassing functional capacity, psychological status, and frequent rehospitalizations may be particularly important to patients (Nieminen, Dickstein et al. 2015) The EQ-5D is a validated, standardized instrument developed by EuroQol.
Tertiary/Exploratory		

OBJECTIVES	ENDPOINTS	JUSTIFICATION FOR ENDPOINTS
To compare the effects on the occurrence of death, hospital readmission for HF or worsening HF (WHF) through day 31	The composite of WHF, death, or hospital readmission for decompensated HF at day 31. WHF is defined as worsening signs and/or symptoms of HF that require an intensification of intravenous therapy (including initiation or re-initiation or dose increase) for HF or mechanical ventilatory, renal or circulatory support (occurring between 24 hours after randomization and the earlier of discharge or day 7).	WHF has been shown to be associated with longer hospital stay and increased risk of HF readmission and death, and HF readmission and death are outcomes representing disease progression. The composite is a generally accepted endpoint in AHF trials.

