8.3.4 Time Period and Frequency for Event Assessment and Follow-Up

The Investigator will record all reportable events with start dates occurring any time after informed consent is obtained until day 31 or the last day of study participation. At each study visit, the investigator will inquire about the occurrence of AE/SAEs since the last visit. Events will be followed for outcome information until resolution or stabilization.

The occurrence of an adverse event (AE) or serious adverse event (SAE) may come to the attention of study personnel during study visits and interviews of a study participant presenting for medical care, or upon review by a study monitor.

All AEs including local and systemic reactions not meeting the criteria for SAEs will be captured on the appropriate case report form (CRF). Information to be collected includes event description, time of onset, clinician's assessment of severity, relationship to study product (assessed only by those with the training and authority to make a diagnosis), and time of resolution/stabilization of the event. All AEs occurring while on study must be documented appropriately regardless of relationship. All AEs will be followed to adequate resolution.

Any medical condition that is present at the time that the participant is screened will be considered as baseline and not reported as an AE. However, if the study participant's condition deteriorates at any time during the study, it will be recorded as an AE.

Changes in the severity of an AE will be documented to allow an assessment of the duration of the event at each level of severity to be performed. AEs characterized as intermittent require documentation of onset and duration of each episode.

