9.4.3 Analysis of the Secondary Endpoint(s)

Treatment groups will be compared with respect to the occurrence of a WHF adverse event, or HF readmission, or death from any cause from randomization through day 91 with a log-rank test stratified by study center. The time to event will be calculated as the date of the first occurrence of any of the component events minus the date of randomization plus 1. If a patient has no component event by day 91, the time to event will be censored at the earlier of 90 days after randomization or the day of last available follow-up.

The changes in EQ-5D-5L index value and in EQ-VAS from randomization to day 7, will be compared between treatment groups using an appropriate contrast at day 7 from a mixed model for repeated measures (MMRM) for each outcome that includes the effects of the baseline value (EQ-5D-5L index or EQ-VAS as applicable), study center, treatment, visit, baseline value×visit and treatment×visit. EQ-5D index will be derived for each patient from the French value set. Patients who are missing a response due to death will be assigned the index value equivalent to death (0) and worst possible VAS score (0). The method assumes that missing data are missing at random (MAR) and the hypothetical treatment effect that is estimated is what would have been observed if all patients had continued on the assigned treatments for the full treatment period. Shifts in responses to each dimension from baseline to each time point will also be described.

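### The first secondary endpoint counts worsening-heart-failure adverse events through day 91, but the section that governs their reporting stops at day 31 and the general adverse-event section is ambiguous

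*Protocol*

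**What the plan says.** The endpoint is defined the same way in three places.

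- Protocol 1.1 (Synopsis): "Time to first event of WHF adverse event, death, or hospital readmission for decompensated HF to day 91".
- Protocol 3 (Objectives and Endpoints): "The composite of first event of a WHF adverse event, hospital readmission for HF, or death through day 91".
- Protocol 9.4.3: groups are compared on the "occurrence of a WHF adverse event, or HF readmission, or death from any cause from randomization through day 91", by a center-stratified log-rank test. For a patient without an event, "the time to event will be censored at the earlier of 90 days after randomization or the day of last available follow-up". There is no separate cut-off for the WHF component.

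Two sections govern how WHF reaches the database.

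- Protocol 8.1.5 takes the WHF component of this endpoint from all adverse events of WHF. The sentence just before that reads: "The investigator will report all events of worsening signs and/or symptoms of heart failure occurring through day 31 as an adverse event".
- Protocol 8.3.4 has reportable events recorded if they start "any time after informed consent is obtained until day 31 or the last day of study participation". The same section also requires every adverse event on study to be documented, and any deterioration during the study to be recorded as one.

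Protocol 8.1.6 carries deaths and rehospitalizations, with the primary reason for readmission, to 90 days after randomization.

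On duration, the synopsis gives "13 months (including recruitment (12 months), Follow up (1 month for the last patient enrolled" for the study and 91 days for each participant.

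**The concern.** The endpoint asks for WHF adverse events over 90 days after randomization, while the section specific to WHF asks investigators to report them for 30. A site that follows 8.1.5 has no instruction to look for WHF in the remaining 60 days. A site that follows the wider sentences in 8.3.4 may record it.

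Two things are at stake. First, a patient who has WHF after day 31, without readmission or death, would be analysed as event-free and at risk up to day 90. If that patient is later readmitted for heart failure, the event is counted, but at the readmission date and not at the earlier onset of WHF. Second, WHF recorded after day 31 would depend on each site's habit. Treatment is open-label, and Protocol 4.2 defends that choice by the objectivity of the outcomes. Investigator-reported WHF is less objective than death or a hospital stay, so uneven reporting could differ by arm. Nothing in the protocol shows that it will.

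The milder events are the most exposed. Section 3 deliberately widened WHF beyond events that need intensified intravenous therapy or mechanical support, and such events are the least likely to surface as a hospital stay.

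**Working it through.** **Step 1. Endpoint horizon against collection window, by component.**

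| Component | Endpoint runs to (1.1, 3, 9.4.3) | Collection runs to | Source |
|---|---|---|---|
| Death | day 91 | 90 days after randomization | 8.1.6 |
| HF readmission | day 91 | 90 days after randomization, with reason | 8.1.6 |
| WHF adverse event | day 91 | day 31; ambiguous in general rule | 8.1.5; 8.3.4 |

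Two components match the horizon. The third does not.

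**Step 2. Share of follow-up time without a clear instruction to report WHF.** Day 31 is 30 days after randomization and day 91 is 90 days after.

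- (90 − 30) / 90 = 60/90 = 66.7%.
- Counting the day of randomization as day 1: (91 − 31) / 91 = 60/91 = 65.9%.
- With the ±5-day visit windows in the schedule: (85 − 35) / 85 = 58.8% at the low end. At the high end it is (90 − 25) / 90 = 72.2%, because the analysis censors at 90 days.

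**Step 3. Time is not events.** The protocol gives no WHF rate over 90 days, so the share of WHF events after day 31 cannot be computed from it. If the WHF hazard is assumed to decay exponentially with half-life h, and λ = ln 2 / h, the share with onset between 30 and 90 days is

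(e^(−30λ) − e^(−90λ)) / (1 − e^(−90λ)).

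- h = 15 days: (0.250 − 0.0156) / (1 − 0.0156) = 24%.
- h = 30 days: (0.500 − 0.125) / (1 − 0.125) = 43%.
- h = 60 days: (0.707 − 0.354) / (1 − 0.354) = 55%.
- Constant hazard: 67%.

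These half-lives are assumptions, not protocol figures. The constant-hazard case fits badly with the background in Protocol 2.1, which reports early worsening of 10–14% at day 7. Carried forward at a constant rate, that gives 1 − 0.90^(90/7) = 74% to 1 − 0.86^(90/7) = 86% by day 90. The shares also cover all late WHF; only those without HF readmission or death are lost to the composite.

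**Step 4. Effect on stated power.** The protocol states no event count or power for this composite. Its one power figure, about 80% for day 7 CRP, reproduces: with 60 per group, a log difference of −ln 0.6 = 0.511 and an SD of 1.002, power is 79.7% by the normal approximation and 79.1% by the t-test. It does not involve WHF.

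**Step 5. Study duration.** Twelve months of recruitment plus about 3 months (90 days) for the last patient is about 15 months, against 13 in the synopsis.

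**The case against.** The strongest reply is that Protocol 8.3.4 already covers the gap. Participation lasts 91 days, so the last day of participation can be read as day 91, and the same section asks for all on-study events and any deterioration. The schedule also marks clinical outcomes at the day 91 call. This stands in part: a reader might infer that WHF after day 31 is not collected at all, and the documents do not support that. They support a contradiction. The general wording does not clearly override the WHF-specific sentence in 8.1.5, and it can equally mean day 31 or an earlier exit.

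Other stronger readings also fail.

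- *The schedule's adverse-event row shows no collection at day 91.* That row is an arrow whose span is lost in the extracted text, so it proves nothing either way. The 30-day adverse-event tabulation in 9.4.4 is a safety-analysis window and does not define endpoint collection.
- *The endpoint cannot be derived.* It can. Deaths and rehospitalizations run to 90 days, and 8.1.6 counts an unplanned overnight stay even without formal admission. The possible loss is late WHF with no such stay for heart failure and no death.
- *The longer timeframe adds nothing for WHF.* Even a day 31 window is more than four times the 7-day limit that section 3 compares it with (30/7 = 4.3), and the definition is looser.
- *Patients enrolled late would miss day 91 because the study lasts 13 months.* Sections 4.4, 9.4.6 and 10.1.2 all require follow-up through the last scheduled contact, so the duration line has no effect on data.

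A statistical analysis plan may exist, and 9.4.1 lets it prevail on analyses. It could restate the endpoint, but it cannot supply events that nobody was asked to report.

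**Conclusion.** The protocol is wrong as written on this point. The WHF component of the first secondary endpoint runs through day 91, while 8.1.5 ends its reporting at day 31 and 8.3.4 leaves the matter open. On the 8.1.5 reading, 60 of 90 days (67% of follow-up time) have no systematic capture of WHF that leads to neither HF readmission nor death, and those patients remain event-free in the risk set. The effect on event numbers or power cannot be stated, because the protocol gives no WHF rate; the hazard scenarios only illustrate a range. Differential reporting by arm is possible in an open-label trial but is not shown.

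The damage is confined to under-ascertainment of one component of one secondary endpoint in a pilot trial. The primary endpoint and the sample size are unaffected. The 13-month study duration is a separate slip in wording.

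**What to change.** Align 8.1.5, 8.3.4 and the Schedule of Activities (1.3) so that WHF adverse events, with onset date, are elicited and recorded through day 91 in both arms, using the existing Visit 6 telephone call. In 8.3.4, replace the either-or end point with one stated window. The cost is one question, one case report form field and amendment wording.

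If late WHF can no longer be collected, restate the endpoint in 1.1, 3 and 9.4.3 as WHF adverse event through day 31, or HF readmission or death through day 91, and say in the analysis how the two windows enter the log-rank test. The exploratory composites in 9.4.9 already state a WHF window apart from the overall horizon, so the form exists. This costs wording only, but gives up late WHF.

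Correct the synopsis study duration to about 15 months, with about 3 months of follow-up for the last patient.

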8.1.6 Other clinical outcomes

Deaths will be recorded through 90 days post-randomization. The primary cause will be recorded when possible. Every effort (consistent with all applicable laws and regulations) will be made to obtain vital status on all randomized subjects.

The length of stay in an intensive care unit (ICU) or other acute care unit and the total length of hospital stay will be recorded for the initial hospitalization and of each rehospitalization through 90 days following randomization. The primary reason for the readmission to the hospital will be recorded. A rehospitalization is defined as an unplanned overnight stay in the hospital, regardless of whether the patient was admitted.

8.1.7 Laboratory assessments

Blood samples (plasma) for central laboratory assessment will be taken at Visit 1 prior to randomization, at 72 hours and day 7 (\pm 1 day) as well as day 31. Samples will be collected in EDTA sample collection tubes and handled as described in the study's Laboratory Procedures manual. Sample aliquots will be stored frozen locally until shipped for longer-term storage and analysis. Unused samples will be discarded within 5 years after the study's completion.

Other lab assessments will be made according to local clinical practice. This should include at a minimum hemoglobin, WBC count, lymphocyte count, sodium, potassium, glucose, liver and kidney

function tests before randomization, day 7 (\pm 1 day), as well as day 31. Any assessments done at 24 hours (day 2) and/or 72 hours (day 3) should be recorded but are not required.

8.1.8 EQ-5D-5L questionnaire

The EQ-5D is a standardized instrument developed by the EuroQoL Group (www.euroqol.org) that measures health-related quality of life (The Euroqol Group 1990). The EQ-5D consists of two pages, which should take only a few minutes to complete (Oppe, Rabin et al. 2008). The first page asks the patient to indicate his/her health state for each of 5 dimensions (mobility, self-care, usual activities, pain/discomfort and anxiety/depression). The second page asks the patient to rate his/her health on a vertical visual analogue scale (EQ-VAS), where the endpoints are labeled “Best imaginable health state” at the top and “Worst imaginable health state” at the bottom. The 5-level EQ-5D version (EQ-5D-5L), introduced in 2009, increased the number of possible response levels to each health dimension from 3 to 5.

The patient will be asked to complete the EQ-5D-5L questionnaire at Visits 1 (randomization), Visit 4 (day 7), and Visit 5 (30 days post-randomization) in a quiet, private space prior to any invasive or demanding study or routine procedures, e.g., blood draws, by using the official linguistically validated translation of the EQ-5D-5L. See appendix in section 12.1 for sample English version (not to be used in the study).

8.2 SAFETY AND OTHER ASSESSMENTS

Safety will be assessed at each study visit. In addition to assessment of signs and symptoms during physical examination, safety will be assessed through local laboratory values obtained as standard of care and per protocol. The occurrence of any adverse events will also be elicited through non-directive questioning of the patient at each study visit and through recording of any event spontaneously reported by the patient or noted by the investigator.

8.3 ADVERSE EVENTS AND SERIOUS ADVERSE EVENTS

8.3.1 Definition of Adverse Events (AE)

Adverse event (AE) means any untoward medical occurrence in a patient or clinical investigation subject administered a pharmaceutical product and which does not necessarily have to have a causal relationship with this treatment (ICH E2A).

Adverse drug reactions (ADRs) include all noxious and unintended responses to a medicinal product related to any dose. The phrase "responses to a medicinal product" means that a causal relationship between a medicinal product and an adverse event is at least a reasonable possibility, i.e., the relationship cannot be ruled out.

An unexpected adverse drug reaction is an adverse reaction, the nature or severity of which is not consistent with the applicable product information.

8.3.2 Definition of Serious Adverse Event (SAE) or Adverse Drug Reaction

A serious adverse event (experience) or reaction is any untoward medical occurrence that at any dose:

- results in death,
- is life-threatening, NOTE: The term "life-threatening" in the definition of "serious" refers to an event in which the patient was at risk of death at the time of the event; it does not refer to an event which hypothetically might have caused death if it were more severe.
- requires inpatient hospitalization or prolongation of existing hospitalization,
- results in persistent or significant disability/incapacity,
- is a congenital anomaly/birth defect, or
- is an important medical event that may not be immediately life-threatening or result in death or hospitalization but may jeopardize the patient or may require intervention to prevent one of

the other outcomes listed in the definition above. These events should also usually be considered serious. Examples of such events are intensive treatment in an emergency room or at home for allergic bronchospasm; blood dyscrasias or convulsions that do not result in hospitalisation; or development of drug dependency or drug abuse.

